4.0 Study Design

One cycle equals 28 days.

This study is an open-label, two-arm or possibly 3-arm, phase II trial. CPX-351 is administered as approximately a 90-minute infusion on days 1, 3, and 5 with one study arm receiving 50 units/m² and the other receiving 75 units/m². Both the 50 and the 75 unit/m² dose levels are considered to have acceptable safety based on observations from a pair of randomized Phase II studies conducted in adult patients, where the observed 60-day mortality results in patients considered fit for intensive chemotherapy and with no prior history of stem cell transplant, was observed to be reduced compared to control.

Patients with newly diagnosed AML who are predicted to be at high risk (30-50%) for induction mortality (death by day 60) are eligible. Every patient entered must have at least one AML-related factor (adverse cytogenetics, secondary AML, MDR phenotype, etc.) that contributes to elevated risk of induction mortality. Patients may or may not have patient-related factors (poor performance status, co-morbidities, poor organ function, etc.) that also contribute to elevated risk of induction mortality. 30 patients will be randomized with a 1:1 ratio to the two dose arms with 15 patients per arm to assess for safety and efficacy. If safety is demonstrated for both of the sub-MTD dose levels, and escalation is deemed feasible above 75 units/m², a cohort of 15 patients will be studied at 100 units/m², the MTD dose level. The latter dose (i.e., 100 units/m²) was found safe and an additional 25 patients will be enrolled at this dose (for a total of 40 evaluable patients) to define efficacy at this standard dose.

At the end of the study a single dose level will be confirmed to have acceptable safety if the observed rate of dose limiting toxicity (DLT) is <5 DLT/15 patients.<33%). Dose limiting toxicity is defined as induction mortality (death occurring during the first 60 days from start of study therapy), grade 3 or 4 non-hematologic toxicity, or dose limiting

hematologic toxicity at least possibly related to the study drug occurring during the first 60 days from the start of study therapy (i.e., during the first cycle of therapy).

For non-hematologic toxicity the following are counted as dose limiting toxicities only under the conditions noted:

- Liver toxicity: Grade 4, related to the study drug, not resolving to grade 2 within 7 days.

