- Decrease in ejection fraction: Grade ≥ 3 (nadir LVEF $<40-20\%$), related to study drug
- Creatinine elevation: Grade ≥ 3 , related to study drug.
- Any other adverse event of Grade ≥ 3 , related to study drug that in the opinion of the PI is inconsistent with the expected adverse events with standard chemotherapy.

Dose limiting hematologic toxicity is defined by bone marrow and peripheral blood examination at Day ≥ 56 showing:

- Absence of recurrent or persistent leukemia AND
- Persistently hypocellular marrow ($<20\%$ cellularity) AND
- Peripheral blood:
 - ANC < 500 and/or
 - Platelet count $< 10,000$

If more than one dose level is considered acceptably safe, the decision about which one to use for future clinical study will be based on efficacy. Efficacy success for an individual patient is defined as achievement of CR or CRI. Observation of ≤ 3 CR or CRI among 15 patients ($\leq 20\%$) defines a non-efficacious study arm. In situations where both study arms are considered equally safe, the study arm with the higher rate of response will be recommended for future study, provided it equals or exceeds 20%.

When the dose recommended for future study is defined, 10 additional newly diagnosed patients will be treated at that dose level (not to exceed a total of 25 patients at that dose level) to obtain additional evidence of safety and efficacy among previously untreated patients with high risk of induction mortality.

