# Responses (inclusive)	
5	0
10	0-1
15	Always stop with this many patients

Toxicity monitoring

In addition, toxicity will be monitored closely. Denote the probability of toxicity by T_E , where toxicity is defined as DLTs. We assume toxicity rate beta (0.66, 1.34) for the experimental treatment in this study. Our safety monitoring rule is described as follows: $\Pr(T_E > 0.33 | \text{data}) > 0.85$. That is, we will stop the enrollment in one dose if, at any time during the study, we determine that there is more than 85% chance that the DLT rate is more than 33% in that dose. Stopping boundaries corresponding to this stopping rule is listed in table 8. For example, the enrollment in one dose will be stopped if the first 4 of the first 5 patients experienced toxicity in that dose.

Table 8: Stopping boundaries for toxicity monitoring for the initial cohort of each dose (n=15)

# Patients (in complete cohorts of 5) (inclusive)	Stop the enrollment in dose level if there are this many DLTs total in that dose level:

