# DLTs (inclusive)	
5	4-5
10	6-10
15	Always stop with this many patients

The operating characteristics for this design are presented in table 9. If the enrollment in one dose continues until 15 patients are evaluated in each arm and 5 CR or CRi are observed, then the 95% credible interval for the response rate would be (11.6%, 47.7%).

Table 9: Operating characteristics of the initial cohort of each dose (n=15)

True CR+CRi Rate	True DLT Rate	Early Stopping Probabilities	Average sample size treated
0.05	0.1	0.931	6.47
0.05	0.2	0.932	6.46
0.05	0.33	0.938	6.39
0.05	0.5	0.959	6.12
0.1	0.1	0.784	88.13
0.1	0.2	0.787	8.10
0.1	0.33	0.804	7.94
0.1	0.5	0.872	7.30
0.2	0.1	0.462	11.1
0.2	0.2	0.468	11.0
0.2	0.33	0.512	10.66
0.2	0.5	0.681	9.33
0.3	0.1	0.229	13.01
0.3	0.2	0.237	12.95
0.3	0.33	0.30	12.5
0.3	0.5	0.543	10.67
0.3	0.6	0.735	9.08
0.4	0.1	0.098	14.11
0.4	0.2	0.108	14.04
0.4	0.33	0.181	13.50
0.4	0.5	0.465	11.42
0.4	0.6	0.691	9.61

If three dose arms continue until 15 patients in each arm evaluated, the toxicity profile and response will be summarized for them. The dose chosen for further study will be the dose with the highest CR+CRi rate, provided that toxicity profile are also acceptable. The probability of correctly selecting the superior dose for different success rate scenarios in the three arms is summarized in table 10 below [Simon R et al 1985].

Table 10: Probability of the best arm being chosen

True Response rate in Superior Dose	True Response rate in inferior Dose 1	True Response rate in inferior Dose 2	Probability of the best arm is chosen

30%	10%	10%	86%
30%	15%	15%	71%
40%	25%	25%	63%
40%	30%	25%	56%
40%	30%	30%	50%
50%	25%	25%	83%
50%	30%	25%	78%
50%	30%	30%	73%
50%	40%	30%	59%
60%	25%	25%	94%
60%	30%	25%	91%
60%	30%	30%	89%
60%	40%	30%	79%
60%	50%	30%	63%

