The arm with a favorable toxicity profile and/or a favorable might be chosen for further evaluation by expanding a cohort of 10 additional patients in that arm. We will use the same criteria (e.g. expansion will be stopped if $\Pr(T_E > 0.33 | \text{data}) > 0.85$) to monitor toxicity for the expansion cohort by using a total sample size of 25 for the winner arm. The stop boundaries are summarized in the following table. If 10 or more patients out of the 1st 20 patients experienced DLT, the trial will be stopped and no expansion cohort will be evaluated. If 10 or more patients out of 20 patients experienced DLT (by adding 5 more patients to the 15 patients in that arm), the expansion will be stopped.

Table 11. Toxicity monitoring for the expanded cohort at a dose of 75 units/m²

# Patients (in complete cohorts of 5) (inclusive)	Stop the arm with expansion cohort if there are this many dose limiting toxicities total:

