	# Toxicities (inclusive)
5	4-5
10	6-10
15	8-15
20	10-20
25	Always stop with this many patients

Expansion of arm with the dose of 100 units/m²

Up to additional 25 patients will be enrolled in this arm, thus total sample size for this arm is up to 40. Assuming that the success rate is binomially distributed, 40 patients will have has 99% power to detect a difference of 5% vs. 30% in success rate at a one-sided type I error rate of 0.05 using an exact test.

Similar futility and toxicity monitoring rules listed above will also be applied for the expansion of arm with 100 units/m². That is, the trial will be stopped early if

$$\Pr(\theta_E < 0.25 + \theta_S | \text{data}) > 0.98 \text{ for futility}$$

or

$$\Pr(T_E > 0.33 | \text{data}) > 0.95 \text{ for toxicity}$$

where θ_E represents the response rate for experimental drug in this study and θ_S represents the response rate for the standard practice (null hypothesis). T_E represents DLT rate. For trial simulation, we use the same assumption for prior distributions listed above for each parameter. That is, θ_S has a prior distribution of beta (10, 190), θ_E has a non-informative flat prior beta(0.1, 1.9), and T_E has a prior distribution of beta (0.66, 1.34).

Table 12 and 13 present the corresponding stopping boundary and operating characteristics (OCs).

Table 12: Stopping boundaries for futility and toxicity of the expansion cohort with the dose of 100 units/m²

N patients evaluated	Stop for toxicity if >= this number of patients experience DLT	Stop for futility if <= this number of patients achieve CR/Ci
5	4-5	0
10	7-10	0
15	9-15	0-1
20	11-20	0-2
25	13-25	0-3
30	15-30	0-4
35	17-35	0-5
40	19-40	0-6

Table 13: OCs of the expansion cohort with the dose of 100 units/m²

True CR+CRi Rate	True DLT Rate	Early Stopping Probabilities	Average sample size treated
0.05	0.1	0.9965	8.16
0.05	0.2	0.9965	8.14
0.05	0.33	0.9969	7.99
0.05	0.5	0.999	7.26
0.1	0.1	0.9294	13.16
0.1	0.2	0.930	13.10
0.1	0.33	0.9372	12.63
0.1	0.5	0.9803	10.19
0.2	0.1	0.5119	25.54
0.2	0.2	0.5156	25.39
0.2	0.33	0.5654	24.00

0.2	0.5	0.8637	16.36
0.3	0.1	0.2029	33.50
0.3	0.2	0.209	33.30
0.3	0.33	0.2903	31.31
0.3	0.5	0.7774	20.23
0.4	0.1	0.0817	37.19
0.4	0.2	0.0887	36.96
0.4	0.33	0.1824	34.70
0.4	0.5	0.7436	22.12
0.4	0.6	0.9612	14.02

Statistical methods:

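### Section 4.0's safety criterion and Section 10's expansion toxicity boundaries do not fit together, and Table 13 does not show how well the added patients at 100 units/m² are protected

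*Combined protocol and SAP*

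**What the plan says.** Section 4.0 gives the only numeric definition of acceptable safety: the "observed rate of dose limiting toxicity (DLT) is <5 DLT/15 patients.<33"%). It is worded as an end-of-study confirmation. The section then chooses among acceptably safe doses on response, and continues: "When the dose recommended for future study is defined, 10 additional newly diagnosed patients will be treated at that dose level", up to 25 in total.

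Section 10.0 selects the dose with the highest response rate, "provided that toxicity profile are also acceptable", without a count. Its expansion paragraph is looser still: "The arm with a favorable toxicity profile and/or a favorable might be chosen for further evaluation". Toxicity in the expansion is judged on all patients in the arm, old and new, by Pr(T_E > 0.33 | data) > 0.85. The text spells out the look: "If 10 or more patients out of 20 patients experienced DLT (by adding 5 more patients to the 15 patients in that arm"), the expansion is halted. Table 11 stops at 8 or more of 15 and 10 or more of 20; its row at 25 is simply the end of accrual.

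For 100 units/m², Section 4.0 reports that the dose proved safe and adds 25 patients. Section 10.0 says: "Similar futility and toxicity monitoring rules listed above will also be applied for the expansion of arm", with the toxicity cut-off raised to 0.95. Table 12 gives DLT boundaries of 11/20, 13/25, 15/30 and 17/35 before the maximum of 40. Table 13 is captioned as the operating characteristics of that expansion cohort.

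**The concern.** An expansion begins only after an arm has looked acceptable. A cumulative rule then carries 15 reassuring patients into every later look, so new patients must do very badly before it reacts. The question is whether the rule can stop an expansion that the plan's own safety criterion has let through, and whether the published operating characteristics tell the reader how likely that is.

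The setting makes this relevant. Eligible patients have a predicted 30-50% risk of death by day 60, and death within 60 days is itself a DLT. A dose with a true DLT rate of 40% shows at most 4 DLTs in 15 about 22% of the time, so a falsely clean first 15 is not a remote event.

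**Working it through.** **Inputs.** Prior: "We assume toxicity rate beta (0.66, 1.34) for the experimental treatment in this study" (Section 10.0, toxicity monitoring). Cut-offs: 0.85 (initial cohorts and 25-patient arm) and 0.95 (100 units/m²). Looks: complete cohorts of 5. Entry: at most 4 of 15 (Section 4.0). For 100 units/m² the actual count is not given, so at most 4 of 15 is an assumption inferred from the statement that the dose was safe.

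**1. Reproducing the plan's boundaries.** After x DLTs in n patients the posterior is Beta(0.66 + x, 1.34 + n − x). The boundary is the smallest x with Pr(T_E > 0.33) above the cut-off. This returns every toxicity boundary in Tables 8, 11 and 12. The boundaries are calculated correctly.

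**2. The 10-patient expansion, Section 4.0 entry.** Worst case at n = 20: 4 + 5 = 9. The posterior is Beta(9.66, 12.34), giving Pr(T_E > 0.33) = 0.8495, below 0.85. Ten of 20 gives 0.930. Since 9 < 10, the look cannot stop the arm at any true DLT rate, and accrual would continue at 9/20 = 45%.

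**3. The 10-patient expansion, Section 10 entry.** Table 11 lets 5, 6 or 7 of 15 continue. The look at 20 then needs 5, 4 or 3 DLTs in the next 5. At a true rate of 50% the probabilities are 1/32 = 3%, 6/32 = 19% and 16/32 = 50%. The look works, but only for arms that Section 4.0 does not call safe.

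**4. The 100 units/m² expansion.** From 4 of 15:
- n = 20: at most 9, boundary 11, so unreachable.
- n = 25: needs 13 − 4 = 9 of 10 new patients.
- n = 30: needs 15 − 4 = 11 of 15.
- n = 35: needs 17 − 4 = 13 of 20.

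Binomial counts were carried forward five patients at a time, removing paths that hit a boundary. Summed over looks 20 to 35, the chance of a toxicity stop is:

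| True DLT rate | Chance of at most 4 of 15 | Stop, from exactly 4/15 | Stop, averaged over at most 4/15 |
|---|---|---|---|
| 33% | 41% | 0.4% | 0.2% |
| 40% | 22% | 2.4% | 1.6% |
| 50% | 5.9% | 14.1% | 11.4% |
| 60% | 0.9% | 42.9% | 38.9% |

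**5. Table 13.** Treating response and DLT as independent, the same recursion over looks 5 to 35 reproduces the 50% DLT rows: 0.7774 (mean size 20.23) at 30% response and 0.7436 at 40%. These figures include futility stopping, which at a 10% DLT rate accounts for nearly all of the tabulated 0.2029 and 0.0817. They also include the looks at 5, 10 and 15, which an arm entering expansion has already passed. The first look alone, 4 or more of 5, stops 6/32 = 18.8% at a 50% rate.

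**6. Sensitivity to the look schedule.** If the criterion were checked after every patient, the 10-patient expansion could stop from 4 of 15, for example at 10/21 (0.904) or 10/22 (0.872). At a 50% DLT rate it would do so about 10% of the time from exactly 4 of 15, and 7.8% averaged over at most 4. For 100 units/m² from 4 of 15 the figure would be about 24%.

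**The case against.** A reader might infer that the expansion rule can never fire and that expansion patients have no protection. The documents do not support that. The under-5-in-15 criterion appears only in Section 4.0, tied to the end of the study; Section 10 states no count for entry, and under its own wording the look at 20 is reachable. Section 10 also says the criterion applies at any point during the study, which could mean per-patient checks. The cohort-of-5 tables and the summary sent to the IND Office Medical Monitor after every 5 patients per arm favour the five-patient reading, but the text is not settled. That review, the power in Section 4.9 to stop for unacceptable toxicity, and serious adverse event reporting all operate independently of the boundaries.

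A reader might also infer that Table 13 is wrong. It is not: it is a correct unconditional calculation, and setting 74-78% beside 11-14% does not compare like with like. The entry criterion is itself a strong screen, since a dose with a 50% DLT rate meets it only 5.9% of the time.

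Finally, a posterior that seldom stops after reassuring data is normal behaviour for this kind of rule. That is fair, but it does not explain why the plan presents an expansion look that its own safety definition makes unreachable, or why the caption points to a cohort that the figures do not describe.

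**Conclusion.** The point holds as an inconsistency between sections and a gap in the reported operating characteristics. Either Section 4.0 governs entry, and the only tabulated look in the 10-patient expansion is inert; or Section 10 governs, and a dose with 5 to 7 DLTs in 15 may be expanded although Section 4.0 does not call it safe. The passages must be reconciled on either reading.

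For 100 units/m², protection of the 25 added patients is slight at true DLT rates up to 50% (a toxicity stop about 11% of the time) and moderate at 60% (39%), although a 60% dose would rarely get that far. This rests on looks every 5 patients and on entry with at most 4 of 15, which is inferred. Because clinical oversight continues alongside the boundaries, this should be fixed but does not invalidate the design.

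**What to change.** 1. Reconcile Section 4.0 with Section 10's expansion paragraph and Table 11, so that one numeric DLT criterion governs entry to expansion.
2. State whether the posterior is checked every 5 patients or continuously.
3. Relabel Table 13 as whole-arm, and add toxicity operating characteristics conditional on entering expansion, for both expansions.
4. Keep the cumulative rule and add a supplementary posterior check on expansion patients only. One option restarts from the stated Beta(0.66, 1.34) prior with the existing cut-offs: 4 or more of 5 for the 10-patient expansion; 4/5, 7/10, 9/15 or 11/20 for 100 units/m². At true DLT rates of 50%, 33% and 20% the first stops 19%, 4% and 0.7% of the time; the second 49%, 8% and 0.8%.

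The cost is a wording change and an added table, with no extra patients. The supplementary check sets aside the first 15 patients' data, carries a 4-8% chance of stopping a dose exactly at the 33% limit, and is only a modest gain for the 10-patient expansion, where it has a single look. Other boundaries would serve, provided their conditional operating characteristics are reported.

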	# Toxicities (inclusive)
5	4-5
10	6-10
15	8-15
20	10-20
25	Always stop with this many patients

Expansion of arm with the dose of 100 units/m²

Up to additional 25 patients will be enrolled in this arm, thus total sample size for this arm is up to 40. Assuming that the success rate is binomially distributed, 40 patients will have has 99% power to detect a difference of 5% vs. 30% in success rate at a one-sided type I error rate of 0.05 using an exact test.

Similar futility and toxicity monitoring rules listed above will also be applied for the expansion of arm with 100 units/m². That is, the trial will be stopped early if

$$\Pr(\theta_E < 0.25 + \theta_S | \text{data}) > 0.98 \text{ for futility}$$

or

$$\Pr(T_E > 0.33 | \text{data}) > 0.95 \text{ for toxicity}$$

where θ_E represents the response rate for experimental drug in this study and θ_S represents the response rate for the standard practice (null hypothesis). T_E represents DLT rate. For trial simulation, we use the same assumption for prior distributions listed above for each parameter. That is, θ_S has a prior distribution of beta (10, 190), θ_E has a non-informative flat prior beta(0.1, 1.9), and T_E has a prior distribution of beta (0.66, 1.34).

Table 12 and 13 present the corresponding stopping boundary and operating characteristics (OCs).

Table 12: Stopping boundaries for futility and toxicity of the expansion cohort with the dose of 100 units/m²

N patients evaluated	Stop for toxicity if >= this number of patients experience DLT	Stop for futility if <= this number of patients achieve CR/Ci
5	4-5	0
10	7-10	0
15	9-15	0-1
20	11-20	0-2
25	13-25	0-3
30	15-30	0-4
35	17-35	0-5
40	19-40	0-6

Table 13: OCs of the expansion cohort with the dose of 100 units/m²

True CR+CRi Rate	True DLT Rate	Early Stopping Probabilities	Average sample size treated
0.05	0.1	0.9965	8.16
0.05	0.2	0.9965	8.14
0.05	0.33	0.9969	7.99
0.05	0.5	0.999	7.26
0.1	0.1	0.9294	13.16
0.1	0.2	0.930	13.10
0.1	0.33	0.9372	12.63
0.1	0.5	0.9803	10.19
0.2	0.1	0.5119	25.54
0.2	0.2	0.5156	25.39
0.2	0.33	0.5654	24.00

0.2	0.5	0.8637	16.36
0.3	0.1	0.2029	33.50
0.3	0.2	0.209	33.30
0.3	0.33	0.2903	31.31
0.3	0.5	0.7774	20.23
0.4	0.1	0.0817	37.19
0.4	0.2	0.0887	36.96
0.4	0.33	0.1824	34.70
0.4	0.5	0.7436	22.12
0.4	0.6	0.9612	14.02

Statistical methods:

Data analysis will be performed using SAS or S-plus, as appropriate. For each arm, the CR/CR_i rate and the DLT rate will be estimated with 95% confidence intervals. The intent-to-treat patients will be used for the primary efficacy analysis, patients who lost-to-follow up in the first 2 cycles will be treated as failures. Patients who received at least one dose of the treatment drug will be evaluable for toxicity outcomes. In addition, Fisher's exact test will be used to compare the response rate and toxicity rate between the two dose levels. For the exploratory objectives, Fisher's exact test will be used to compare immune responses between different doses of CPX-351. Two-sample t test or ANOVA or Fisher's exact test will be used to check the association between Troponin - T and cardiotoxicity, and t test or ANOVA will be used to compare the apoptosis of ex-vivo cultured leukemia cells.

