3.3 Exploratory Objectives

To investigate the effect of CPX-351 on immune response, as determined by the effect on recovery of functional pathogen-specific and leukemia-specific immune responses and the recovery and function of NK cells.

To investigate the role of Troponin-T as an early marker for CPX-351-induced cardiotoxicity.

To investigate ex vivo the cytotoxicity of combination of Pim kinase inhibitor(s) and CPX-351 on circulating leukemia cells.

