16.0 APPENDIX 6: Immune reconstitution after chemotherapy with CPX-351

Immune reconstitution is believed to constitute a major element that determines the risk of relapse and the possibility of late infectious complications. Immune reconstitution after standard cytarabine and anthracycline combination has not been well studied and not at all after therapy with CPX-351. To this effect we propose the following:

To determine how CPX-351 influences the recovery of functional pathogen-specific and leukemia-specific immune responses.

We will conduct analyses of T cell phenotype, estimate antigen-specific T cell precursor frequencies (by intracellular cytokine flow cytometry and peptide/dextramer staining) and determine antigen-specific cytokine production capacity (cytokine bead array assay). We will evaluate antigen-specific T cell recovery following treatment with CPX-351 by analyzing 1) Immunophenotypic recovery of Th1, Th2, Th17 and regulatory T cells; 2) The number and function of recovering CMV and Flu-specific T cells capable of responding functionally to in vitro stimulation with overlapping pools of peptide by intracellular cytokine detection; 3) The number and function of T cells capable of responding to leukemia-associated antigens including proteinase 3 (PR3), Wilms tumor antigen (WT1) and cancer testis antigens (e.g. PRAME) will be assessed following stimulation with overlapping pools of peptide and intracellular cytokine assay.

To determine how CPX-351 influences the recovery and function of NK cells

To evaluate if CPX-351 will impact on NK phenotype and function, we will conduct longitudinal analyses of NK phenotype and function during CPX-351 therapy.

Quantitative 10-color flow cytometric analysis will be performed to 1) characterize the functional phenotype of NK cells using an extended panel of antibodies against activating (NKp30, NKp44, NKp46, NKG2D, NKG2C, DNAM1) and inhibitory receptors (NKG2A and KIRs); 2) assess the effector function of NK product against MHC class I-deficient leukemia targets and primary AML cells from the recipient by intracellular cytokine assay for interferon-gamma (IFN- γ) production, chemokine production including CCL3 (MIP1 α) and CCL4 (MIP1 β) and cytotoxicity, including CD107a degranulation and 51chromium release assay; Confocal microscopy will be used to directly assess the immune synapse formation with leukemia targets.

Sample collection and distribution

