60 cc of blood (Green top tubes- heparin) and 5 cc in purple top (EDTA) to be collected at 3 time points:

- 1- Before induction with CPX-351
- 2- At recovery from induction, just prior to consolidation #1
- 3- At recovery from 1st cycle of consolidation just prior to consolidation #2

Samples will be sent to [name] lab manager, P14.3144; [contact].

17.0 APPENDIX 7: Early Detection of CPX-351-induced cardiotoxicity using high sensitivity troponin T

Chemotherapy is an effective treatment in most cancers. Yet all these drugs have a various range of side effects. Chemotherapy-induced organ injury remains a major issue in cancer patient care. Chemotherapy-induced cardiotoxicity is the most serious one, particularly associated with the use of anthracyclines, ultimately impacting the long-term cancer survivors and survival time. CPX-351 is a liposomally encapsulated combination of cytarabine and daunorubicin. The liposomal encapsulation may lead to a decrease in cardiac toxicity. However, the CPX-351-induced cardiotoxicity has not been evaluated.

Identification of chemotherapy-induced cardiac toxicity has been dependent on imaging modalities, such as echocardiogram or MUGA scan. Despite their usefulness, routine cardiac imaging alone lacks sensitivity for early detection of subclinical cardiac disease. Multiple cardiac biomarkers have been evaluated extensively in both animal models and clinical studies such as creatine kinase (CK), creatine kinase – MB fraction (CK-MB), troponin T (cTnT), troponin I (cTnI), brain natriuretic peptide (BNP), C-reactive protein (CRP), and interleukin family member (ST2).^{5, 6} In acute coronary syndromes, troponin is one of the most well established biomarkers used to guide diagnosis and treatment. However, the utility of biomarkers in monitoring myocardial damage secondary to chemotherapy is still controversial.

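### Fisher's exact test between doses is the only method named for serial, quantitative immune measures that are collected to describe recovery

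*Combined protocol and SAP*

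**What the plan says.** Section 3.3 gives the aim as the "effect on recovery of functional pathogen-specific and leukemia-specific immune responses and the recovery and function of NK cells". Appendix 6 lists the measurements. They include T-cell phenotype, precursor frequencies, "The number and function of recovering CMV and Flu-specific T cells", antigen-specific cytokine production, and NK phenotype and cytotoxicity by quantitative flow cytometry and release assays. For NK cells it adds that "we will conduct longitudinal analyses of NK phenotype and function during CPX-351 therapy".

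Blood is "to be collected at 3 time points". The first is "Before induction with CPX-351", the second "At recovery from induction, just prior to consolidation #1", and the third after the first consolidation, before the second. The evaluation table in Section 6.2 gives the same three occasions. Footnote 7 of Appendix 1 differs: it adds the start of a second induction where one is given, and every consolidation.

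The statistical methods in Section 10.0 cover this objective in one sentence: Fisher's "exact test will be used to compare immune responses between different doses of CPX-351". The same paragraph assigns a t test or ANOVA to ex-vivo apoptosis, another laboratory readout, and includes them among the options for troponin T.

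**The concern.** The named test does not match what is collected in three respects.

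- **Scale.** Fisher's test needs categories and the assays return quantities. Without a prespecified category, someone must choose a cut-point later, possibly after seeing the data.
- **Target.** The objective is how immune function recovers within patients after treatment. A between-dose test asks whether doses differ. If all doses suppress and restore immunity alike, there is no dose difference to find, yet recovery is still the quantity of interest.
- **Population.** The second and third Appendix 6 samples are tied to consolidation, and Section 4.6 restricts consolidation to patients in CR or CRi. A dose comparison at those times is conditional on response.

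At stake is whether a small set of optional samples can answer the question for which they are drawn.

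**Working it through.** **1. What is left undefined.** Sections 3.3, 6.2 and 10.0 and Appendix 6, read together, do not define an immune response as a category, give a cut-point, name the time point to be compared, say how the pre-induction sample is used, or specify a method for the longitudinal analyses.

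**2. Figures available.** The plan gives no sample size, power, SD or effect size for the immune analysis, so it has no figure to reproduce. The arm size can be checked. With n = 15 and success at 3 or more responses, the exact binomial gives P(X ≥ 3 | 0.05) = 0.036 and P(X ≥ 3 | 0.30) = 0.873. This matches the stated 87% power within the 0.05 limit.

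**3. Patients behind the later samples.** At the 30% response rate of the design alternative, 15 × 0.30 = 4.5 and 40 × 0.30 = 12 patients respond. Over an assumed range of 20-50%, this is 3 to 7.5 of 15 and 8 to 20 of 40. These are ceilings. Under Section 4.6, transplant may replace chemotherapy consolidation and CRi with low counts receives none. The samples are also optional.

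**4. Cost of dichotomising.** For a median split of normal data, the large-sample relative efficiency is 2/π = 0.64. For small samples, simulation was used: 4,000 replicates, two-sided 0.05, normal baseline and follow-up values, an assumed 1 SD dose difference at follow-up, and assumed baseline correlations of 0.3 / 0.5 / 0.7. Cut-points lie midway between the true arm means, or between the mean changes.

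| Patients per arm | Fisher, follow-up value | Fisher, change from baseline | t test, follow-up value | ANCOVA with baseline |
|---|---|---|---|---|
| 15 v 15 | 39-41% | 28 / 39 / 64% | 75-76% | 77 / 85 / 95% |
| 15 v 40 | 68-69% | 52 / 68 / 89% | 89-90% | 92 / 96 / 99.6% |
| 5 v 12 | 21-23% | 16 / 22 / 35% | 41-42% | 43 / 50 / 65% |
| 5 v 5 | 13-14% | 9 / 13 / 23% | 29% | 28 / 32 / 44% |

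With no dose difference at 15 v 15, Fisher's test rejects in 1.3-1.8% of trials against a nominal 5%. Part of its loss is therefore conservatism from discreteness.

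**5. Discreteness at 5 v 5.** For 5/5 against 1/5, two-sided p = 2 × C(5,1)/C(10,6) = 2 × 5/210 = 0.048. For 5/5 against 2/5, p = 2 × C(5,2)/C(10,7) = 2 × 10/120 = 0.17. The arms must differ by at least four of five patients to reach 0.05.

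**6. A change common to both doses.** Suppose both doses shift every patient's expected value by 1 SD from baseline (correlation 0.5, cut-point at the baseline mean). A paired t test pooled over doses detects this in 80%, 99% and 99.9% of trials at 5, 10 and 15 per arm. Fisher's test between doses rejects in 0.2%, 0.5% and 1.7%. That is correct behaviour, because the doses do not differ. It shows that the test addresses a different question.

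**The case against.** A reader might infer that Fisher's test necessarily ignores baseline and cannot test recovery. The documents do not support that. If each patient were classed as recovered or not against their own pre-induction sample, the test would use baseline, could combine visits, and would compare recovery proportions between doses. Nor must the outcome be yes/no, since versions for larger tables exist. The defect is that no such category is defined. Even with one, the test would compare doses and would not estimate recovery shared by them, and step 4 shows less power than ANCOVA on the same data.

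It can also be said that the Section 10.0 sentence covers only the dose comparison, and that Appendix 6 already promises longitudinal NK analyses and an evaluation of T-cell recovery. This stands as evidence of intent, but no method is given.

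The efficiency of 0.64 is not specific to this plan. It assumes normality, a median split and large samples, and the plan specifies no median split. The simulated powers rest on assumed effects. Both are illustrations of size.

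A reader might also infer that all post-induction results concern responders only. Under Appendix 6 that is too broad, because the sampled group is patients who start consolidation, not all responders. Under footnote 7 of Appendix 1 it is wrong, because Section 4.5 offers a second induction to patients whose marrow is not leukemia-free.

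Finally, the objective is exploratory and the samples optional. No stopping rule or dose selection in Section 10.0 uses them.

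**Conclusion.** The concern holds in limited form. The only named method fits neither the scale of the measurements nor the stated aim of recovery, and the category it would need is not defined. Under the assumed 1 SD difference at 15 per arm, the planned test has roughly half the power of a simple continuous analysis. With about 5 per arm, all the between-dose tests are weak (9-44%), so the dose comparison should be treated as exploratory whichever method is used. Bias from a cut-point chosen late is a risk, not something shown. Because the later Appendix 6 samples come only from patients who start consolidation, dose comparisons there are not comparisons of the groups as randomised. This is a low-severity point, and the primary CR/CRi analysis does not depend on it.

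**What to change.** Replace the Fisher sentence in Section 10.0 as follows.

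- Analyse each immune measure on a continuous scale, for example after log transformation.
- Describe recovery by within-patient change from the pre-induction sample, pooled over doses, with confidence intervals. Paired tests within each arm are not a good fallback: with five patients, the exact two-sided Wilcoxon signed-rank test cannot go below 2/2^5 = 0.0625.
- Compare doses, as exploratory, with a baseline-adjusted model: ANCOVA at a named time point, or a mixed model with time and dose.
- If Fisher's test is kept, predefine a baseline-referenced recovery category and the time point at which it is judged.
- State that the Appendix 6 post-induction samples represent patients who start consolidation, so dose comparisons there are conditional on response.
- Reconcile the immune sampling times in Section 6.2 and Appendix 6 with footnote 7 of Appendix 1.

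The analysis changes need only SAP wording and use the same data. They cost slightly more analysis work and some reliance on a model in a small sample.
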